### 8.1 Sample Size Considerations and Power Analysis:

**Sufficient Power for RCT:** Given timeline and resources proposed for this pilot RCT, we anticipate recruiting N=138 participants. We expect that 58% will have adherence  $\leq 95\%$ , leaving N=80 to be randomized. We conducted a Monte Carlo simulation in Mplus with N = 5000 replications, assuming a total randomized sample of N=80, 25% attrition, proper handling of missing data, standardization of all analysis variables, and that baseline adherence, age, sex, side effects, cognitive/executive functioning, seizure type, and SES (covariates) will explain at least 40% of the post-treatment adherence error variance (based on our pilot data and previous studies) Our analysis indicates that we will have at least 80% power to detect a post-treatment group difference effect size of  $d > 0.62$  in adherence rates (i.e., approximately 15% difference in group adherence rates at post-treatment). Effect sizes for recently published social norms interventions have ranged from 0.41 to 0.85 when compared to those without social norms comparisons, and we have sufficient power to detect effects within the range of those published. The estimates of preliminary efficacy and variability of our social norms intervention that we obtain will be used to power for a future larger trial.

**Randomization:** At 1 month, we will randomize all patients who demonstrate adherence  $\leq 95\%$  to either the control group (i.e., reminders, feedback) or treatment group (i.e., reminders, feedback with social norms comparisons) using stratified block randomization with two strata and blocks of size 2 or 4 chosen randomly within each stratum. Stratification will be based on

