#### 4.4 Statistical Design and Power

**Aim 1: Examine the feasibility, accessibility, acceptability, and responsiveness of a mHealth social norms intervention to improve AED adherence for adolescents with epilepsy.** H1: Adolescents with epilepsy will rate the intervention as highly feasible, easy to use, acceptable, and responsive to their needs.

*Analyses Aim 1: We will examine means and standard deviations of ratings completed by adolescents on the Adapted Feasibility and Acceptability Questionnaire, Revised Website/mHealth tool Evaluation Questionnaire (WEQ), and System Usability Scale. For the Adapted Feasibility and Acceptability Questionnaire, ratings of 3-4 are considered good. The WEQ is primarily qualitative in nature and will be used during Phase 1b modifications, as well as the RCT to obtain qualitative data on the use of the social norms mHealth tool. Finally, scores on the System Usability Scale ranging from 80-100 range indicate good to excellent usability.*

**Aim 2: Examine the preliminary efficacy of the mHealth social norms intervention on AED adherence, seizure severity, and HRQOL in adolescents with epilepsy.** H2a: Participants in the treatment group will demonstrate statistically significant *improvements* in adherence with corresponding medium/large effect sizes compared to the control group at post-treatment. H2b: Greater improvements in seizure severity, HRQOL, and adherence are expected at 3-month follow-up for the treatment versus control group.

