**Power:** For the focus group and extended formative usage evaluation (ORBIT Phase 1a and 1b), we will use qualitative data analysis to modify the mHealth tools. A sample size of 10 for usability is sufficient to detect 95% of usability problems when pilot testing an mHealth tool.

Given timeline and resources proposed for this pilot RCT (ORBIT Phase II), we anticipate recruiting N=138 participants. We expect that 58% will have adherence  $\leq 95\%$ , leaving N=80 to be randomized. We conducted a Monte Carlo simulation in Mplus with N = 5000 replications, assuming a total randomized sample of N=80, 25% attrition, proper handling of missing data, standardization of all analysis variables, and that baseline adherence, age, sex, side effects, cognitive/executive functioning, seizure type, and SES (covariates) will explain at least 40% of the post-treatment adherence error variance (based on our pilot data and previous studies) Our analysis indicates that we will have at least 80% power to detect a post-treatment group difference effect size of  $d > 0.62$  in adherence rates (i.e., approximately 15% difference in group adherence

rates at post-treatment). Effect sizes for recently published social norms interventions have ranged from 0.41 to 0.85 when compared to those without social norms comparisons, and we have sufficient power to detect effects within the range of those published. The estimates of preliminary efficacy and variability of our social norms intervention that we obtain will be used to power for a future larger trial.

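### The plan claims sufficient power across published effects of d = 0.41 to 0.85, but its own simulation supports 80% only from about d = 0.62; at 0.41 power is about 46%

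*SAP*

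**What the plan says.** SAP 4.4 (Power) and Protocol 8.1 (Sample Size Considerations and Power Analysis) carry the same power text for the randomised phase. A Monte Carlo simulation was run in Mplus "assuming a total randomized sample of N=80, 25% attrition, proper handling of missing data", and on the basis that the covariates "will explain at least 40% of the post-treatment adherence error variance". The result is given as "at least 80% power to detect a post-treatment group difference effect size of" d > 0.62, which the plan equates to roughly 15 percentage points of adherence.

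The next sentence turns to the literature: "Effect sizes for recently published social norms interventions have ranged from 0.41" to 0.85. It ends with the claim "and we have sufficient power to detect effects within the range of those published". It does not repeat the 0.62 limit, and no power is given for any other effect size.

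Hypothesis H2a predicts a statistically significant improvement "in adherence with corresponding medium/large effect sizes compared to the control group at post-treatment". Neither document states the alpha level or whether the test is one- or two-sided.

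**The concern.** The two sentences do not agree. A design with 80% power only from d = 0.62 upward does not have that power for effects between 0.41 and 0.62. That stretch is (0.62 − 0.41)/(0.85 − 0.41) = 0.21/0.44, or 48% of the published range.

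The lower end is also the more relevant one. The Protocol's Background describes the 0.41 result as coming from adolescents given physical-activity feedback relative to peers, against feedback on their own behaviour only. That is close to this trial's contrast, where both arms receive individual feedback and one adds social norms. The 0.85 result concerns academic performance.

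H2a is judged by statistical significance. A reader who takes the sentence at face value would expect a true effect of 0.41 to be detected reliably, and might read a non-significant result as evidence against the intervention. At that effect size, significance is roughly an even chance.

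**Working it through.** **Inputs from the plan.** 80 randomised; 25% attrition, so 80 × 0.75 = 60 observed; covariates explain R² = 0.40; seven named covariates; ANCOVA on post-treatment adherence; equal allocation, implied by two arms in blocks of 2 or 4.

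**Assumptions.** Two-sided alpha 0.05. Covariate degrees of freedom k = 7 to 9, since seizure type or SES may need more than one term.

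**Step 1: reproduce the plan's figure.** For a standardised outcome with n = 60, the standard error of the adjusted difference is

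SE = √[(1 − R²) × (4/n) × (n − 3)/(n − 3 − k)]

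The last factor is the precision lost by estimating k covariate coefficients. With k = 7:

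SE = √[0.60 × 0.0667 × 57/50] = √0.0456 = 0.2135

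At d = 0.62 the non-centrality is 0.62/0.2135 = 2.90. On n − 2 − k = 51 degrees of freedom the critical value is 2.008, and the non-central t gives 81% power. The 80% threshold is d = 0.610, 0.616 and 0.623 for k = 7, 8 and 9. The plan's 0.62 therefore reproduces.

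**Step 2: same model, other effect sizes.** At d = 0.41 with k = 7, the non-centrality is 0.41/0.2135 = 1.92, below the critical value, so power is under one half.

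| d | k = 7 | k = 8 | k = 9 | Simulation (5,000 replicates, t-test, 7 covariates) |
|---|---|---|---|---|
| 0.41 | 47.0% | 46.2% | 45.4% | 47.4% |
| 0.50 | 63.2% | 62.3% | 61.4% | 62.4% |
| 0.62 | 81.3% | 80.5% | 79.6% | 81.2% |
| 0.85 | 97.4% | 97.2% | 96.9% | 97.3% |

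**Step 3: scale from the plan's own point.** This needs only the stated 80% at 0.62 and an alpha. Power at d is Φ[(1.960 + 0.842) × d/0.62 − 1.960].

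- d = 0.41: Φ(1.853 − 1.960) = 46%
- d = 0.50: Φ(2.259 − 1.960) = 62%
- One-sided 0.05, with 1.645 in place of 1.960: 50% at 0.41 and 64% at 0.50

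**Step 4: sensitivity at d = 0.41.**

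| Choice | Power at 0.41 |
|---|---|
| Closed form, no allowance for estimating covariates, two-sided | 52-54% |
| Maximum likelihood z-test on all 80, two-sided, with or without auxiliary variables | 55-59% |
| One-sided 0.05, closed-form and maximum likelihood variants | 58-68% |
| No attrition (contrary to the plan), two-sided | 59-66% |
| No attrition and one-sided | 71-77% |

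None reaches 80%. For 80% power at 0.41 with 60 observed and a two-sided test, the covariates would have to explain about 73-74% of the variance, against the 40% assumed.

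**The case against.** The sentence can be read narrowly, as saying only that the detectable effect of 0.62 falls inside 0.41 to 0.85. That is true, and the threshold stands one sentence earlier. But the wording refers to effects within the range and follows directly on both endpoints, so the narrow reading is not the natural one.

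The 46% is conditional. Alpha and sidedness are unstated, the primary hypothesis is worded directionally, and the planned analysis is maximum likelihood on all 80 participants rather than a t-test on 60. A two-sided maximum likelihood z-test gave 55-59% at 0.41. It also gave 86% or more at 0.62, which is compatible with a claim of at least 80%. This stands as a limit on precision. Against it, that z-test had a type I error of 7.3% in simulation, and if 0.62 is the 80% point, scaling gives about 46% two-sided whichever test is used.

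The d = 0.50 figure rests on the usual convention for a medium effect, which the documents do not define, so it is an illustration only.

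Finally, this is a pilot. The sample size follows from timeline and resources, and the results are meant to inform a larger trial. That limits the consequence but does not make the sentence correct.

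**Conclusion.** The concern holds. The statement of 80% power from d = 0.62 is sound; the claim of sufficient power for the published range is wrong for effects from 0.41 to about 0.62. The best estimate at 0.41 is about 46%, assuming two-sided alpha 0.05 and taking 0.62 as the 80% point. With the planned attrition, the alternatives examined run up to 68%. That power at 0.41 is well short of 80% does not depend on these choices. If medium in H2a means d = 0.50, that effect is also below the threshold, at about 62%. The error is one of reporting: it should be corrected, but it does not undermine the design or the analysis.

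**What to change.** In both SAP 4.4 and Protocol 8.1, replace the claim about the published range with wording such as: *The trial has 80% power for d of about 0.62 or more (about 15 points). Power is lower for smaller effects in the published range: about 62% at d = 0.50 and about 46% at d = 0.41.* Take the final values from the sponsor's existing Mplus simulation, rerun at 0.41 and 0.50, and state the alpha level and sidedness used.

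The cost is one sentence in two documents and two further simulation runs. The sample size does not change. The stated power becomes less favourable.
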